## **Study Protocol**

### *Trial design*

A care provider and participants blinded, parallel, randomized controlled trial with three groups was completed from September 2022 to April 2023. This trial is reported according to the CONSORT 2010 checklist for randomized controlled trials. All procedures were approved by the Ethics Committee of the Polytechnic Institute of Coimbra (CEIPC 6/2022).

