### *Outcomes and testing procedures*

Before (T0) and after 12-weeks (T1) of interventions and control procedures, concentric and eccentric peak torque (PT) of IR and ER of the dominant and non-dominant shoulder was performed through an isokinetic dynamometer Biodex System 3 (Biodex Medical Systems, New York), at 60°/s, 120°/s and 180°/s.

Previously to strength evaluations, each swimmer did a 10-minute warm-up of a general upper limb joint mobilization. The isokinetic dynamometer assessment was carried out with the swimmer in the supine position. Half of the swimmers started the assessment with the dominant shoulder, and the other half started with the non-dominant shoulder. Previously, this order was randomized for each swimmer. The upper extremity was positioned with the shoulder abducted to 90° and the elbow flexed to 90° so that the dynamometer's axis was aligned with the longitudinal axis of the humerus. The athlete's trunk and evaluated arm were stabilized using velcro straps to avoid compensatory movements (Fig. 3). Gravity correction was not used for this testing position because the ER and IR shoulder muscles moved with and against gravity as they applied force. Strength was tested through 145° of range of motion (ROM), between 80° of ER and 65° of IR, to obtain the PT variation in the maximum rotational ROM available. The tests started every time with the shoulder in 80° of ER. The concentric strength was tested first, followed by the eccentric strength test. The order of the angular velocity test was increased (60°/s-120°/s-180°/s) to preserve an ascending difficulty during the evaluations. A hard cushion deceleration control was selected to allow the subject the greatest availability of velocity attainment before deceleration. The procedure was explained to all athletes before the start of testing, with emphasis on exerting maximal effort within an individual's tolerance. After this, swimmers performed 3 submaximal trials to familiarize themselves with the ROM and the accommodating resistance of the dynamometer. Both concentric and eccentric tests at different velocities consisted of 5 maximal-effort reciprocal repetitions. Standardized verbal instructions and encouragement were given to all subjects. A minute rest period between different tests was preserved.

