The PT was used to characterize the strength values of shoulder rotator muscles, defined as the maximum torque produced by the shoulder at any point of the ROM. To analyze shoulder rotator strength balance, the ER:IR ratio was calculated – the quotient between PT values of the ER:IR multiplied by 100. For this investigation, the conventional concentric ER : concentric IR ratio and functional eccentric ER : concentric IR were calculated.

**Fig. 3.** Subject position and stabilizing during the isokinetic dynamometer strength assessment.

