### *Sample size*

The G\*power software (Franz Faul, Edgar Erdfelder, Axel Buchner, Universitat Kiel, Kiel, Germany, version 3.1.9.4) was used to calculate the sample size, considering an alpha level of 0.01, a power of 0.99, and an effect size (Cohen's *d*) of 2.81 based in a similar previous study. Thus, a minimum of 24 swimmers – 8 for different groups – was necessary.

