### *Randomisation and blinding*

An initial screen survey was carried out on the two swimming teams before the sample selection. After the application of eligibility criteria, the eligible swimmers were divided into a weight program group, an elastic band program group, or a control group. The allocation to each group was performed through stratified randomization according to the team, sex, and main swimming style. This design was used to equate the possible effects of these three variables in results and was prepared with a computer random number generator by a member of the research team. Then, all swimmers carried out the T0 assessment moment through the isokinetic dynamometer. To minimize fatigue bias during the assessments, half of the swimmers started the evaluation with the dominant shoulder, and the other half started with the non-dominant shoulder. Previously, this order was randomized for each swimmer. After T0 moment, for 12-weeks the two experimental interventions were applied and supervised by a blinded sports physiotherapist external to the study, without knowledge of the previous procedures and the study objectives. It only explains in detail the interventions and the load that should be used by each athlete considering the 1RM test previously performed by a member of the research team. The participants were unaware of the existence of other sample groups. At the end of the 12-weeks, all swimmers who

completed the proposed interventions carried out the T1 strength assessment through the isokinetic dynamometer. All T0 assessment procedures were maintained in T1 moment.

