## **Statistical Analysis Plan**

The data was previously filtered (smoothing option) and windowed at 95% of test velocity. Data analysis was performed using the Acqknowledge 4.1 software. The mean and standard deviation (SD) of the PT assessments in the 5 repetitions of different muscles (IR and ER), actions (concentric and eccentric), and angular velocities (60°/s, 120°/s, and 180°/s) for both sides were calculated. Subsequently, the conventional concentric ER : concentric IR ratio and the functional eccentric ER : concentric IR ratio were verified for these three angular velocities.

All statistical analysis was carried out using IBM SPSS Statistics 27 software. Mean and SD were used for sample characterization. The Shapiro-Wilk test was used to verify the normality of the sample distribution. The homogeneity of variance between the three groups was verified for the sample characterization variables and the main outcome at T0, through the One-Way ANOVA or the Kruskal-Wallis tests. After this, an inter-group analysis in T0 and T1 and an intra-group analysis between T0 and T1 was made for dominant and non-dominant shoulders. For an inter-group analysis, the One-Way ANOVA or the Kruskal-Wallis tests were applied to compare differences between the three groups in T0 and T1. For an intra-group analysis, the Paired Sample T-test or the Wilcoxon test was applied to compare differences in each group between T0 and T1. A p-value  $\leq 0.05$  was considered as the level of significance for each difference in PT and ER:IR ratios.

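### The SAP judges each of 36 outcomes at p≤0.05 without adjustment, does not identify its main outcome, and names no comparison that separates a programme from control

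*Combined protocol and SAP*

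**What the plan says.** The section Outcomes and testing procedures measures "concentric and eccentric peak torque (PT) of IR and ER of the dominant and non-dominant shoulder" at three angular velocities, before (T0) and after (T1) the 12 weeks. From the torques it derives two ratios: "the conventional concentric ER : concentric IR ratio and functional eccentric ER : concentric IR were calculated", each being "the quotient between PT values of the ER:IR multiplied by 100". No measure is ranked above another.

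In the Statistical Analysis Plan, one-way ANOVA or Kruskal-Wallis "tests were applied to compare differences between the three groups in T0 and T1". Paired t-tests or Wilcoxon tests then compare T0 with T1 inside each group. Both analyses cover both shoulders. The threshold of p≤0.05 "was considered as the level of significance for each difference in PT and ER:IR ratios". A main outcome is mentioned once, in connection with the baseline check between groups, and is not identified there or anywhere else. No adjustment, testing order or pairwise comparison is given.

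The Sample size section concludes that "a minimum of 24 swimmers – 8 for different groups – was necessary", from an alpha of 0.01, power of 0.99 and Cohen's d of 2.81. It does not name the outcome behind that d.

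**The concern.** The T1 between-group tests are the only planned tests that compare randomised groups after treatment. There are 36 of them, each with its own 5% chance of a false positive. The plan does not say beforehand which result, or what pattern of results, would count as evidence that a programme works. A chance finding on one torque at one velocity in one shoulder could be reported as a gain in strength or balance.

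The tests are also three-group tests. A significant one says that the groups are not all alike. It does not say whether weights, bands or both differ from control, or only from each other. Crediting a named programme needs a further comparison that the plan does not specify.

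**Working it through.** **1. The plan's own figure.** For a two-sided, two-sample t-test at alpha 0.01 with d = 2.81, exact power is 0.9903 with 8 per group and 0.9722 with 7. So 8 × 3 = 24, and the stated minimum is reproduced. It is the size for one two-group comparison on one outcome.

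**2. Number of outcomes** (from the outcomes section and the SAP).
- Peak torque: 2 muscles × 2 actions × 3 velocities × 2 shoulders = 24.
- Ratios: 2 types × 3 velocities × 2 shoulders = 12.
- Total: 24 + 12 = 36 three-group tests at T1. There are 36 more at T0 and 3 × 36 = 108 within-group tests, which are not counted below.

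**3. Expected false positives at T1 with no effect.** 36 × 0.05 = 1.8, whatever the correlations.

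**4. Chance of at least one.** If the 36 tests were independent: 1 − 0.95^36 = 0.84. They are not independent, so correlated outcomes were simulated: 20,000 trials per setting, three groups of 8, no effect, one-way ANOVA at 0.05. The 24 torques were log-normal with an assumed CV of 25%, and the 12 ratios were computed from them. The correlations are assumptions.

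| Assumed structure of the torques | P(at least one p≤0.05) |
|---|---|
| Common correlation 0 / 0.3 / 0.5 | 0.77 / 0.73 / 0.68 |
| Common correlation 0.7 / 0.9 / 0.95 | 0.61 / 0.54 / 0.51 |
| Moderate to strong muscle, action and side structure | 0.60 / 0.46 / 0.34 |
| Near-perfect structure | 0.23 |
| Velocity and side add nothing (6 distinct outcomes) | 0.16 to 0.21 |
| Action adds nothing either (3 distinct outcomes) | 0.125 |

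A CV of 15% or 35% moved the cases checked by about 1 percentage point. Kruskal-Wallis gave 0.25 to 0.75 outside the last two rows.

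**5. Sensitivity to the model.** If all 36 outcomes share one correlation and the ratios are not derived from the torques, the result is 0.84 at correlation 0, 0.58 at 0.5, 0.20 at 0.9 and 0.14 at 0.95. Other structured models with derived ratios gave 0.42 to 0.69.

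**6. Small clusters.** Because outcomes move together, three or more of the 36 were significant in 12% to 26% of the null trials in step 4.

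**7. Stratified randomisation.** Allocation is stratified by team, sex and main swimming style, but the planned ANOVA ignores the strata, which can make it conservative. Suppose sex is perfectly balanced and explains half the between-swimmer variance. The rates become 0.58 at common correlation 0.5, 0.45 at 0.95, and 0.15 to 0.49 in the structured cases. If sex explains 80%, they are 0.50, 0.44, and 0.12 to 0.43. Three or more significant results then occur in about 3% to 14% of trials.

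**The case against.** The SAP sets a level per comparison and claims no control across the family, so no stated figure is false. It does not expressly rule out adjustment either. That is fair: the fault is a missing decision rule, not a wrong number. It still matters, because the rule as written lets each difference count by itself.

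The percentages rest on correlations and a CV that are not in the documents. This also stands. A reader might infer a definite error rate, or a firm floor, from any one row of the table. Neither is supported. The 0.51 at common correlation 0.95, for example, comes mainly from the ratios: there the torques alone give about 13% and the ratios alone about 44%, because dividing ER by IR cancels what the torques share and leaves residual noise. What does not depend on these assumptions is the count of 36, the expected 1.8 and the absence of a rule.

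The alpha of 0.01 in the sample size calculation might be taken as protection against multiplicity. The documents do not link the two, the analysis uses 0.05, and 0.01 is well above 0.05/36 = 0.0014.

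A broad effect near d = 2.81 would look quite different from a few scattered results. That is true, but the plan does not say in advance which pattern would be accepted.

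Holm across 108 comparisons takes no account of the correlation and is conservative. This is conceded. It is why the fix puts full reporting of estimates first and uses Holm only where a p-value is used to single out a programme.

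**Conclusion.** The concern holds. An isolated p≤0.05 among the 36 T1 tests cannot be read as a programme effect at the 5% level, and a small cluster is not proof either. With no effect and 8 per group, the chance of at least one significant T1 test is about 23% to 77% in the non-degenerate settings, 12% to 21% in the collapsed limits, and 14% to 84% under the alternative models. Stratification could pull these down, to 12% in the lowest non-collapsed case checked, which is still more than twice 5%. Even a genuine three-group difference leaves the responsible programme unidentified.

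A reader might go further and infer that the trial's findings are chance, or that no primary outcome was ever fixed. The documents support neither. They contain no results, and a primary outcome may be on record elsewhere; they show only that this plan does not identify one.

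**What to change.** Replace the last sentence of the SAP with one decision rule:

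> Efficacy is judged only on between-group comparisons at T1. If a record dated before results were seen names a single primary outcome, its three pairwise comparisons are tested with familywise error held at 0.05, and all other outcomes are exploratory. If there is no such record, all 36 outcomes are labelled exploratory and reported in full with pairwise estimates and confidence intervals. No programme is declared effective on an unadjusted p≤0.05, and any p-value used to single out a programme is adjusted as one family across all 108 pairwise T1 comparisons (36 outcomes × 3 pairs), using Holm with exact p-values for rank tests. Three-group, T0 and within-group p-values are descriptive.

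The dated record is needed because the trial "was completed from September 2022 to April 2023", so a primary outcome chosen now could be chosen with the results in view. The pairwise step must itself be adjusted. In simulations with one programme at d = 2.81 on all torques and the other ineffective, Holm on the three-group tests followed by unadjusted pairwise t-tests falsely separated the ineffective programme from control in 13% to 70% of trials. Holm across the 108 did so in 0.6% to 2.2%.

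**Cost.** SAP wording and reanalysis of existing data. The price is power:
- With a documented primary outcome, little is lost at the planned effect. A three-way split gives 0.05/3 = 0.0167 per pair, which is looser than the 0.01 at which 8 per group already has power 0.99 for d = 2.81.
- Without one, the first Holm step is 0.05/108 = 0.00046. Pairwise t-test power with 8 per group is 0.81 at d = 2.81, 0.37 at d = 2.0 and 0.13 at d = 1.5.
- For rank tests with complete separation at 8 v 8, the exact p is 2/C(16,8) = 0.00016, which passes. The asymptotic p is 0.00078, which does not.
- At 7 v 7 even the exact p, 2/C(14,7) = 0.00058, cannot pass. This matters because the swimmers who "completed the proposed interventions carried out the T1 strength assessment through the isokinetic dynamometer" may be fewer than 8 per group.
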